### **6.1.6 Follow-up Visit**

Upon completion of the 14-day treatment period, subjects will return to the site for the Day 21 Follow-up visit, approximately 7 days ( $\pm 1$  day) after the last dose of study drug was administered. Subjects will complete all study assessments and procedures as indicated in the SOA ([Appendix A, Table 2](#)).

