### **9.1. Adverse Events**

Any AE occurring after the date/time of informed consent signature but prior to the first dose of study medication (ie, occurring during the Screening and Baseline periods) will be listed. All AEs that occur after the first dose of study drug will be considered TEAEs. This includes any AEs that started or worsened (if present at baseline, increased in frequency or severity) after taking the first dose of the study drug. For AEs occurring on the date of first dose, if the time of onset is missing, the AE will be assumed to be treatment emergent.

All AEs will be coded using the MedDRA Version 21.1 or higher coding dictionary.

The causal relationship of the AE to the study drug is determined by the investigator as Not Related, Unlikely Related, Possibly Related, Probably Related, and Definitely Related. These will be mapped to Unrelated (*Not Related or Unlikely Related*) and Related (*Possibly Related, Probably Related, and Definitely Related*).

Adverse events severity grades are reported as mild, moderate, or severe.

Summaries of incidence rates (frequencies and percentages) of individual TEAEs will be presented by SOC, PT, and cohort. Such summaries will be displayed for all TEAEs, TEAEs by maximum severity, and TEAEs by relationship.

Each subject will be counted only once within each summation level (SOC and PT). If a subject experiences more than 1 TEAE within each summation level only the TEAE with the strongest relationship or the maximum severity, as appropriate, will be included in the summaries by subject for relationship and severity, respectively. If a particular event is missing the severity and/or relationship, then the strongest possible severity or relationship will be assumed for analysis (severity=severe, relationship = definitely related).

Incidence will be presented by descending frequency of SOC and PT within SOC, and then alphabetically within PT where the incidence is the same.

Missing and partially missing AE start and/or stop dates will be imputed, for the purpose of statistical analysis, according to the specifications described in Section 6.1.9.

Numbers of AEs will also be presented in these AE summary tables.

In the AE data listings, all AEs will be displayed. AEs that are treatment emergent will be flagged.

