## **9.2. Clinical Laboratory Evaluations**

Screening and safety laboratory tests will be performed at Screening, Pre-dose, Day 1, Day 7, Day 14, and at follow-up on Day 21. All laboratory test results will be summarized descriptively by study visit for the Safety Population overall and by cohort as both observed values and change from baseline values for each parameter. Categorical urinalysis results will be summarized using frequencies by study visit and cohort. Levels of composite biomarker panel for renal tubular injury will also be summarized by study visit and listed.

Shifts from baseline for clinical laboratory values below, within, or above the normal range will be provided for hematology and chemistry results by study visit. See Section 6.1.1 for the definition of baseline. Clinically significant abnormal findings will be reported as AEs. Abnormal laboratory results will be listed.

Pregnancy test results will be listed.

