##### **9.5.3.    Columbia Suicide Severity Rating Scale**

The C-SSRS is a questionnaire that prospectively assesses Suicidal Ideation and Suicidal Behavior. At the Pre-dose visit, the "baseline" version of the C-SSRS will be administered. This version assesses Suicidal Ideation and Suicidal Behavior during the subject's lifetime and during the past 12 months. At the Day 14 and Day 21 visits (and the Early Termination visit for subjects withdrawing early), the "since last visit" version will be administered.

Suicidality data collected on the C-SSRS will be listed for all subjects in the Safety Population. Tables will include results from the Suicidal Ideation and Suicidal Behavior sections of the C-SSRS. Frequencies and percentages of subjects with a response of "Yes" at any point on the

Suicidal Ideation and Suicidal Behavior items will be summarized for the Safety Population (overall and by cohort).

Commercially Confidential Information

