Note: Percentages are n/Number of subjects in the Safety Population and respective Protocol Amendment\*100. The C-SSRS scale consists of a Baseline evaluation that assesses the lifetime and more recent experience (past 12 months) of the subject with suicidal ideation and behavior, a baseline evaluation that focuses on suicidality since Screening that occurs before first dose of study drug (all of which is summarized under "pre-treatment"), and a post-baseline evaluation ("post-treatment") administered at either Day 21 visit or early termination visit for discontinued subjects, which focuses on suicidality since the last study visit. Subjects are counted once for each C-SSRS section and once for each C-SSRS item answered "Yes" in pre-treatment and post-treatment.

SOURCE: Listing 16.2.8.6

Commercially Confidential Information

Commercially Confidential Information

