**Listing 16.2.8.6**  
**Columbia-Suicide Severity Rating Scale (C-SSRS)**  
**All Subjects**

Subject ID	Protocol Version	Study Visit	Date of Assessment (Study Day)	Reference Period	Reason not Completed	Category	Assessment	Result
XXXXXX	X.X	XXXXXX	DDMMYYYY (XX)	Baseline/ Screening		Suicidal Ideation	1. Wish to be dead  If yes, describe: 2. Non-Specific Active Suicidal Thoughts  If yes, describe: 3. Active Suicidal Ideation with Any Methods (not Plan) without Intent to Act  If yes, describe: 4. Active Suicidal Ideation with Some Intent to Act, without Specific Plan  If yes, describe: 5. Active Suicidal Ideation with Specific Plan and Intent  If yes, describe: Most Severe Ideation Type # (1-5) Description of Ideation	XX  XX  XX  XX  XX  X XXXXXXXXXXXX XXXX 1 = 1-4 hours/a lot of time 1 = Fleeting – few seconds or minutes 1 = Easily able to control thoughts
						Intensity of Ideation	Frequency	
							Duration	
							Controllability	
						...	...	...

[figure not shown]
Note: All subjects received CAD-1883 300 mg BID. At the Pre-dose visit, the “baseline” version of the C-SSRS was administered. This version assesses Suicidal Ideation and Suicidal Behavior during the subject’s lifetime and during a predefined period. At the Day 21 visit (and the Early Termination visit for subjects withdrawing early), the “since last visit” version was administered.

Study day is calculated relative to the date of the first dose of study drug.

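### The only visible C-SSRS table pools lifetime and recent history into one Pre-treatment count beside a short Post-treatment period, so it does not report new or worsened suicidality and in general cannot identify it

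*SAP*

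**What the plan says.** **The table.** SAP 13.3 and 14.2 show one C-SSRS output, Table 14.3.6.4, for the Safety population by cohort and overall. Redacted text follows it in both places. Each group has a Pre-treatment and a Post-treatment column, with one row per ideation or behavior item plus section rows.

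**What goes into each column.** According to the table note, Pre-treatment includes "a Baseline evaluation that assesses the lifetime and more recent experience (past 12 months) of the subject with suicidal ideation and behavior", together with a pre-dose evaluation covering the time since Screening. Post-treatment is one form, "administered at either Day 21 visit or early termination visit for discontinued subjects, which focuses on suicidality since the last study visit". The counting rule is "Subjects are counted once for each C-SSRS section and once for each C-SSRS item answered" with a Yes, applied within each column. SAP 9.5.3 plans only frequencies and percentages of any positive answer, plus a listing.

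**The listing.** Listing 16.2.8.6 gives each subject's answers by visit, with the reference period, the five ideation items and the most severe ideation type (1 to 5).

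**When the form is given.** SAP 9.5.3 schedules the follow-up version "At the Day 14 and Day 21 visits (and the Early Termination visit for subjects" who withdraw). Protocol 7.12, footnote 25 of the schedule in both documents, and the table note itself do not call for a routine Day 14 form.

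**Other safety data.** For adverse events, SAP 9.1 defines treatment emergence within the subject: "This includes any AEs that started or worsened (if present at baseline, increased in frequency or severity) after taking the first dose". For hematology and chemistry, SAP 9.2 says "Shifts from baseline for clinical laboratory values below, within, or above the normal range will be provided", and SAP 9.3 does the same for blood pressure and heart rate.

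**The concern.** SAP section 9 names the C-SSRS among its safety evaluations. The question for a reader is whether anyone developed ideation or behavior on drug that they did not have before, or had it in a more severe form. Two marginal counts per item do not answer that.

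The pooling makes it worse in two ways. A subject with a positive answer decades ago and another on treatment appears in both columns, exactly like a subject whose recent ideation is unchanged. And because one column covers a lifetime and the other covers days to weeks, the second will usually be smaller whatever the drug does. SAP section 1 allows these outputs to go into study reports and regulatory submissions, where the table may be read without the listing.

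**Working it through.** The documents give no C-SSRS rate or figure, so there is nothing to reproduce. The check is what the two columns can and cannot determine.

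**Inputs.** N = 30 (Protocol 11.2.4, approximately 30). The Pre and Post counts below are assumptions.

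**Bounds.** For one item, let Pre and Post be the numbers with a positive answer in each column. The number positive after baseline but not before lies between max(0, Post − Pre) and min(Post, N − Pre).

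| Pre | Post | Table reads | Possible new onsets |
|---|---|---|---|
| 0 | 1 | 0% then 3.3% | exactly 1 |
| 3 | 0 | 10.0% then 0% | exactly 0 |
| 1 | 2 | 3.3% then 6.7% | 1 to 2 |
| 3 | 2 | 10.0% then 6.7% | 0 to 2 (up to 2/27 = 7.4% of those without a history) |
| 3 | 3 | 10.0% then 10.0% | 0 to 3 |
| 6 | 3 | 20.0% then 10.0% | 0 to 3 (up to 3/24 = 12.5%) |

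**Over a grid.** Take Pre from 0 to 6 and Post from 0 to 3, which is 7 × 4 = 28 combinations. The number of new onsets is fixed in 10: the 7 with Post = 0, and the 3 with Pre = 0 and Post of 1 to 3. Post exceeds Pre in 6 combinations (3 of them already among the 10), which proves at least one new onset. That leaves 28 − 10 − 3 = 15 combinations with at least one Post answer that are equally compatible with no new onset and with some. To prove one new onset when Pre is 1, 3 or 6, Post must reach 2, 4 or 7.

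**How likely is Pre = 0?** With an assumed per-subject lifetime prevalence p for an item, the chance of at least one Pre answer is 1 − (1 − p)^30. For p = 1%, 3%, 5%, 10% and 15% this is 0.26, 0.60, 0.79, 0.96 and 0.99. The exact case is plausible for rare items and unlikely for common ones.

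**New against recent status.** The comparison of most interest is with the past 12 months. The pooled column hides that count, so a recurrence after years without ideation cannot be separated from ideation that was already current.

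**Recall periods for a completer.**
- Counted from the Day 14 visit: the last dose is taken there (Protocol 6.1.4), and follow-up is 7 ± 1 days "after the last dose of study drug was administered", so 6 to 8 days. Twelve months is 365/8 = 46 to 365/6 = 61 times as long.
- Counted from the Baseline form, assumed 1 to 3 days before Day 1, to Day 21 ± 1: (20 − 1) + 1 = 20 to (22 − 1) + 3 = 24 days. Twelve months is then about 15 to 18 times as long.

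The lifetime period is longer still in either case.

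**The case against.** - **The table is sometimes exact.** This stands. If Pre or Post is 0, new onsets are known, and if Post exceeds Pre, at least the difference is new. With about 30 subjects and a period of days to weeks, Post = 0 may well be the result. Even then, a fall from a lifetime count to zero says nothing about the drug.
- **The assumed counts are not from the documents.** This also stands, and they serve only as illustration. Inclusion criterion 6 (otherwise healthy), exclusion 1 and exclusion 25 (uncontrolled psychiatric disorder) may keep Pre low, though none visibly excludes a past history. Redacted criteria might.
- **Marginal counts are ordinary in this SAP.** ECG interpretation, qualitative urinalysis and orthostatic hypotension are also tabulated that way, so the C-SSRS is not the sole exception. Those tables, however, do not set a lifetime beside a few days.
- **The listing already answers the question.** For a reader who goes through it, yes. This limits the harm but does not make the summary table informative. No C-SSRS test is planned, so no formal inference is biased.
- **Dosing days.** A reader might infer that a completer's 14 dosing days fall in neither column, since Pre ends before the first dose and the note starts Post at the last study visit. The documents do not establish this. Protocol 7.12 uses the phrase as the name of a form version, and raters may have asked about the time since the previous C-SSRS. It is a point to clarify.
- **Since Screening.** The current schedule marks no C-SSRS at Screening, which might suggest that the note is wrong. But subjects were enrolled under three amendments, and the listing shell carries a combined Baseline/Screening entry, so a Screening form remains possible.

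**Conclusion.** The point holds as a minor one. Table 14.3.6.4 does not report new or worsened suicidality and, outside the exceptions above, cannot identify it; among the visible outputs only Listing 16.2.8.6 can. A side-by-side reading of its columns leans towards improvement because the recall periods differ by a factor of at least about 15.

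It would go too far to say that the table can never show a new onset, or that the safety conclusions are compromised. The gap is in summary reporting, not in data capture: adverse events are collected throughout (Protocol 7.1), and the primary endpoint of treatment-emergent adverse events is untouched.

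The conclusion rests on the visible text. A redacted output could already supply the comparison, and a redacted exclusion of any lifetime history would make Pre zero and remove most of the problem.

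**What to change.** 1. In Table 14.3.6.4, split Pre-treatment into Lifetime and Past 12 months.
2. Add rows for subjects whose post-baseline ideation or behavior is new, or whose ideation type is more severe, compared with the past 12 months. A small shift table of most severe ideation type (1 to 5) would serve equally well.
3. Use subjects with a post-baseline form as the denominator. The note now divides by the Safety Population, which counts a missing form as a negative answer, while SAP 4.1 uses non-missing data for by-visit displays.
4. State in the note the recall period that the post-baseline form actually used.
5. Align SAP 9.5.3 with Protocol 7.12 and footnote 25 on the Day 14 form.
6. Keep the reference to Screening in the note unless the sponsor confirms that no Screening form was used under any amendment.

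The cost is one table shell, one note and one SAP sentence, made as an SAP amendment or as an added table in the study report. The answers are already collected, so no protocol amendment, extra visit or subject burden follows.

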### 14.3. Planned Listing Shells

Listing 16.2.1.1  
Subject Disposition  
All Subjects

Subject ID	Protocol Amendment	Subject Status	Date of Last Dose (Study Day)	Date of Discontinuation/Completion (Study Day)	Reason for Discontinuation
XXXXXX	1.0	XXXXXXXX	DDMMYY (X)	DDMMYY (X)	
XXXXXX	2.0	XXXXXXXX	DDMMYY (X)	DDMMYY (X)	
XXXXXX	2.0	XXXXXXXX	DDMMYY (X)	DDMMYY (X)	
XXXXXX	3.0	XXXXXXXX	DDMMYY (X)	DDMMYY (X)	XXXXXXXXXX: XXXXXXXX
XXXXXX	3.0	XXXXXXXX	DDMMYY (X)	DDMMYY (X)	XXXXXXXXXXXXXXXXXXXXXX

Note: Study day is calculated relative to the date of first dose of study drug. For pre-dose: study day= Event Date – Date of the first dose of date; For post-dose: study day= Start Date/ Stop Date – first dose date + 1.

**Programming note:** Concatenate specify text with a colon. If reason for early termination is Other, concatenate the specify text as follows: "Other: XXXXXXXXX". If the reason for Discontinuation is Death, then concatenate cause of death and date of death as shown above. If lost to follow-up, concatenate with date of last contact and specify text as follows: "Lost to follow-up: XXXXXX; date of last contact: DDMMYY".

Listing 16.2.1.2  
Visit Status  
All Subjects

Subject ID	Protocol Amendment	Day 7 Visit Status					Day 14 Visit Status					Date of Early Termination (Study Day)
		Complete Day 7 as Scheduled?	If No, Early Terminate from the Study?	Complete the Early Termination Visit?	Day 7 Visit Date (Study Day)	Complete Day 14 as Scheduled?	If No, Early Terminate from the Study?	Complete the Early Termination Visit?	Day 7 Visit Date (Study Day)	Complete Day 14 as Scheduled?	If No, Early Terminate from the Study?	
XXXXXX	X.X	XXX	XXX	XXX	DDMMYYYY (X)	XXX	XXX	XXX	DDMMYYYY (X)	DDMMYYYY (X)	DDMMYYYY (X)	DDMMYYYY (X)
XXXXXX	X.X	XXX	XXX	XXX	DDMMYYYY (X)	XXX	XXX	XXX	DDMMYYYY (X)	DDMMYYYY (X)	DDMMYYYY (X)	DDMMYYYY (X)
XXXXXX	X.X	XXX	XXX	XXX	DDMMYYYY (X)	XXX	XXX	XXX	DDMMYYYY (X)	DDMMYYYY (X)	DDMMYYYY (X)	DDMMYYYY (X)
XXXXXX	X.X	XXX	XXX	XXX	DDMMYYYY (X)	XXX	XXX	XXX	DDMMYYYY (X)	DDMMYYYY (X)	DDMMYYYY (X)	DDMMYYYY (X)

Note: Study day is calculated relative to the date of first dose of study drug. For pre-dose: study day= Assessment Date – Date of the first dose of date; For post-dose: study day= Assessment Date – first dose date + 1.

Listing 16.2.2.1  
Descriptions of Protocol Defined Inclusion and Exclusion Criteria  
All Subjects

Protocol Amendment	Inclusion/Exclusion	Criterion Number	Criteria Description
X.X	Inclusion	1	Adult subjects between 18 and 75 years of age, inclusive, with history of tremor that fulfills the diagnostic criteria of ET according to Movement Disorder Society (MDS) Consensus Statement on the classification of tremors from the task force on tremor of the International Parkinson and Movement Disorder Society
X.X	Inclusion	2	XXXXXXXXXXXX
...	...	...	...
X.X	Exclusion	1	XXXXXXXXXXXX
X.X	Exclusion	2	XXXXXXXXXXXX

***Programming note:*** This listing will be programmed similarly to how SDTM.TI would be created.

**Listing 16.2.2.2**  
**Inclusion and Exclusion Criteria Met/Not Met**  
**All Subjects**

Subject ID	Protocol Amendment	Date (Study Day) of: Informed Consent	All Inclusion Criteria Met?	Any Exclusion Criteria Met?
XXXXXX	X.X	DDMMYY (X)	Yes	No
XXXXXX	X.X	DDMMYY (X)	No: 05, 10	No
XXXXXX	X.X	DDMMYY (X)	No: 05	No
XXXXXX	X.X	DDMMYY (X)	Yes	Yes: 04
XXXXXX	X.X	DDMMYY (X)	Yes	No
XXXXXX	X.X	DDMMYY (X)	Yes	No

Note: Study day is calculated relative to the date of first dose of study drug (= ICF Date – Date of the first dose of date)  
Refer to Listing 16.2.2.1 for inclusion and exclusion criteria text.

***Programming note:*** If more than 1 inclusion or exclusion criterion number exists, concatenate with a comma as shown above.

Listing 16.2.2.3  
Protocol Deviations  
All Subjects

Subject ID	Protocol Amendment	Date (DDMMYYYY) (Study Day)	Event Type	Violation Level	Description
XXXXXX	X.X		XXXXXXXXXXXX XXXXXXXXXXXXXXXX	MAJOR MINOR	XXXXXXX XXXXXXXXXXXXXXXX
XXXXXX	X.X		XXXXXXXXXXXX XXXXXXXXXXXXXXXX	MINOR MINOR	XXXXXXXXXXXXXXXXXXXX XXXXXXXXXXXX
XXXXXX	X.X		XXXXXXXXXXXX	MAJOR	XXXXXXXXXXXXXXXXXXXX

Note: Study day is calculated relative to the date of first dose of study drug. For pre-dose: study day= Event Date – Date of the first dose of date;  
For post-dose: study day= Event Date – first dose date + 1.

***Programming note:*** the structure of this listing may change depending on the information in the protocol deviations file.

Listing 16.2.3  
Analysis Populations  
All Subjects

Subject ID	Protocol Amendment	Analysis Population			CCI	Primary Reason for Exclusion
		Safety [1]	FAS [2]	Exposed [3]		
XXXXXX	X.X	Yes	Yes	Yes		XXXXXXXXXXXXXXXXXX
XXXXXX	X.X	Yes	No	Yes		XXXXXXXXXXXXXXXXXX
XXXXXX	X.X	Yes	Yes	Yes		XXXXXXXXXXXXXXXXXX
XXXXXX	X.X	Yes	Yes	Yes		XXXXXXXXXXXXXXXXXX
XXXXXX	X.X	Yes	Yes	No		XXXXXXXXXXXXXXXXXXXX

Abbreviations: FAS = full analysis set; CCI ; TETRAS-PS = Tremor Research Group Essential Tremor Rating Assessment Scale (TETRAS)- CCI ; TETRAS-PS = Tremor Research Group Essential Tremor Rating Assessment Scale (TETRAS)-performance subscale (PS).

Note: All subjects received CAD-1883 300 mg BID. [1] The Safety population includes all subjects who take at least 1 dose of study drug.

[2] The FAS consists of subjects in the Safety population who had at least 1 post-baseline assessment of both TETRAS-PS CCI .

[3] Commercially Confidential Information

[4] Commercially Confidential Information

**Programming note:** Concatenate all reasons for exclusion with a semi-colon.

Listing 16.2.4.1  
Demographics and Baseline Characteristics  
All Subjects

---

Subject ID	Protocol Amendment	Site	Sex	Child-Bearing Potential?	Date of Birth	Age (years)	Ethnicity	Race	Commercially Confidential Information
XXXXXX	X.X	XXXXXX	XXXX	No	DDMMYYYY	XX	XXXXXX	XXXXXX	
XXXXXX	X.X	XXXXXX	XXXXXX	No	DDMMYYYY	XX	XXXXXX	XXXXXX	
XXXXXX	X.X	XXXXXX	XXXXXX		DDMMYYYY	XX	XXXXXX	XXXXXX	
XXXXXX	X.X	XXXXXX	XXXX		DDMMYYYY	XX	XXXXXX	XXXX	

---

***Programming Note:*** If subject has multiple races, concatenate them.

Listing 16.2.4.2  
Medical History  
All Subjects

Subject ID	Protocol Amendment	System Organ Class/ Preferred Term/ Verbatim Term	Start Date (Study Day)/ End Date (Study Day)/Ongoing
XXXXXX	X.X	XXXXXXXXXXXXXXXXXX/ XXXXXXXXXXXXXXXXXX/ XXXXXXXXXXXXXXXXXX	DDMMYYYY (X)/ DDMMYYYY (X)
		XXXXXXXXXXXXXXXXXX/ XXXXXXXXXXXXXXXXXX/ XXXXXXXXXXXXXXXXXX	MMYYYY (X)/ Ongoing
		XXXXXXXXXXXXXXXXXX/ XXXXXXXXXXXXXXXXXX/ XXXXXXXXXXXXXXXXXX	DDMMYYYY (X)/ Ongoing
XXXXXX	X.X	XXXXXXXXXXXXXXXXXX/ XXXXXXXXXXXXXXXXXX/ XXXXXXXXXXXXXXXXXX	DDMMYYYY (X)/ DDMMYYYY (X)

Note: Study day is calculated relative to the date of first dose of study drug. For pre-dose: study day= Start Date/ Stop Date – Date of the first dose of date;  
For post-dose: study day= Start Date/ Stop Date – first dose date + 1.

Medical history was coded using MedDRA version 20.1. Only subjects with medical history recorded are listed.

[1]

Commercially Confidential Information

**Programming note:** SOC & PT text should be in title case in table, as shown in the shell.

Listing 16.2.4.3  
Disease History  
All Subjects

Subject ID	Protocol Amendment	Date of First ET Symptom (Study Day)	Date of ET Diagnosis (Study Day)	Commercially Confidential Information	ET Triggers		Did Alcohol Use Reduce Tremor Severity?	First or Second-Degree Blood Relative with Prior ET Diagnosis?
					Trigger Type	Frequency		
XXXXXX	X.X	DDMMYYY (XX)	DDMMYYY (XX)	Commercially Confidential Information	XXX	XXX	XXX	XXX
XXXXXX	X.X	DDMMYYY (XX)	DDMMYYY (XX)		XXX	XXX	XXX	XXX
XXXXXX	X.X	DDMMYYY (XX)	DDMMYYY (XX)		XX	XX	XX	XX
XXXXXX	X.X	DDMMYYY (XX)	DDMMYYY (XX)		XX	XX	XX	XX

Abbreviation: ET = Essential Tremor.

Note: Study day is calculated relative to the date of first dose of study drug. For pre-dose: study day= Start Date/ Stop Date – Date of the first dose of date; For post-dose: study day= Start Date/ Stop Date – first dose date + 1.

**Programming note:** Concatenate specify text for Treatment Type, Trigger Type, Frequency Type as shown above if the answer is "OTHER"

Listing 16.2.5.1  
Study Drug Administration  
All Subjects

Subject ID	Protocol Amendment	Study Visit	Administered Proper Dosage of Study Drug?	Reason Dose Not Administered	Date/Time of In-Clinic Administration (Study Day)	Date/Time of Last Dose Prior to Clinic Visit (Study Day)
XXXXXX	X.X	XXXXXXX	Yes	XXXXXXXXXXXXXXXXXX	DDMMYY/HH:MM	DDMMYY/HH:MM
	X.X	XXXXXXX	Yes		DDMMYY/HH:MM	DDMMYY/HH:MM
	X.X	XXXXXXX	Yes		DDMMYY/HH:MM	DDMMYY/HH:MM
	X.X	XXXXXXX	Yes		DDMMYY/HH:MM	DDMMYY/HH:MM
		XXXXXXX	No			
XXXXXX	X.X	XXXXXXX	Yes	XXXXXXXXXXXXXXXXXX	DDMMYY/HH:MM	DDMMYY/HH:MM
	X.X	XXXXXXX	Yes		DDMMYY/HH:MM	DDMMYY/HH:MM
	X.X	XXXXXXX	Yes		DDMMYY/HH:MM	DDMMYY/HH:MM

Note: Study day is calculated relative to the date of first dose of study drug.  
Time for last dose prior to clinic visit is approximate.

Listing 16.2.5.2  
Drug Accountability  
All Subjects

Subject ID	Protocol Amendment	Total Daily Dose	Bottle	Date Dispensed (Study Day)	Number of Capsules Dispensed	Was Bottle Returned to the Clinic?	Date Returned (Study Day)	Number of Unused Capsules Returned
XXXXXX	X.X	300 mg BID	Bottle A	DDMMYYYY (X)	XX	Yes	DDMMYYYY (X)	XX
XXXXXX	X.X	300 mg BID	Bottle A	DDMMYYYY (X)	XX	Yes	DDMMYYYY (X)	XX

Note: Study day is calculated relative to the date of first dose of study drug.

**Programming note:** Concatenate specify text with a colon if the Capsules Dispensed is OTHER.

Listing 16.2.5.3  
Missed Doses  
All Subjects

Subject ID	Protocol Amendment	Were any Doses Missed?	Date of Missed Dose (Study Day)	AM/PM Dose	Number of Pills not Taken	Reason for Missed Dose
XXXXXX	X.X	No				
XXXXXX	X.X	Yes	DDMMYYYY (X)	AM	XX	XXXXXXXXXXXX
XXXXXX	X.X	Yes	DDMMYYYY (X)	PM	XX	XXXXXXXXXXXX

Note: Study day is calculated relative to the date of first dose of study drug (= Date of Missed Dose – first dose date + 1).

Commercially Confidential Information

Commercially Confidential Information

